### 9.3.2 Presentation of Data

For biometrical analysis, data obtained in this trial and documented in the eCRFs will be listed. For parameters of interest, summary tables with descriptive group statistics for metrical variables will be prepared. For categorical / dichotomous variables summary tables showing the absolute and relative count in each category will be prepared.

Full details of the analyses will be defined in the Statistical Analysis Plan (SAP). The SAP will be finalized prior to the respective database lock. The analyses as defined in the SAP will be followed.

If any unforeseen additional analysis is included in the clinical study report it will be clearly flagged as an additional unplanned explorative analysis. The CRO will be responsible for data management and statistical evaluation. Data will be analyzed using SAS®.

GMTs, GMFIs and antibody response rates for RSV-specific humoral immune responses determined from serum and nasal swab samples will be determined as described in [Section 7.1](#) and [Section 1.5](#).

Median and geometric mean SFU/1 x 10^6 PBMC, GMFIs as well as response and responder rates for RSV-specific cellular immune responses will be determined as described in [Section 1.5](#)

Clinical laboratory test results will be marked whether the result is below, within or above the respective reference range. The number of values outside of the corresponding reference range will be counted.

Details for all ECGs will be listed. In addition the central ECG assessment of either normal, normal variant and abnormal as well as the investigator's interpretation as to whether ECGs, assessed as abnormal by the central ECG assessor, are clinically significant or not clinically significant will be summarized.

The occurrence of solicited local and general AEs during the 8-day period post vaccination (Days 0–7) will be summarized on a per subject and per vaccination basis.

Unsolicited AEs will be coded using Medical Dictionary for Regulatory Activities (MedDRA) coding terminology. The intensity of AEs will be graded according to [Section 8.2](#).

SAEs will be listed separately. Each SAE will be described individually in detail.

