6. Women of childbearing potential (WOCBP) must have used an acceptable method of contraception for at least 30 days prior to the first vaccination, must agree to use an acceptable method of contraception (as defined in [Section 8.2.11](#)) during the trial, and must avoid becoming pregnant for at least 28 days after the last vaccination. WOCBP must have a negative serum pregnancy test at screening and a negative urine pregnancy test prior to each vaccination

7. Not clinically significant laboratory values as defined in the protocol, excluding any Grade  $\geq 3$  toxicity.
8. Negative human immunodeficiency virus antibody test (anti-HIV), negative hepatitis B surface antigen (HBsAG) and negative antibody test to hepatitis C virus.
9. Electrocardiogram (ECG) without clinically significant acute findings (e.g. findings suggestive of current ischemia, ventricular arrhythmias, congestive heart failure and ventricular hypertrophy).

Exclusion criteria

1. Pregnant or breast-feeding women.
2. Uncontrolled serious infection, i.e. not responding to antimicrobial therapy.
3. History or current clinical manifestation of any serious medical condition, which in the opinion of the investigator would compromise the safety of the subject or would limit the subject's ability to complete the trial.
  - o History of cerebrovascular disorders, including stroke. Patients with history of transient ischaemic attack (TIA)  $\geq 1$  year prior to trial participation remain eligible.
  - o History of myocardial infarction within  $\leq 1$  year prior to trial participation, current clinical manifestation of angina pectoris, current clinical manifestation of congestive heart failure  $\geq$  New York Heart Association (NYHA) Grade II, uncontrolled high blood pressure defined as systolic blood pressure  $\geq 150$  mmHg and/or diastolic  $\geq 100$  mmHg within the last 2 months.
4. History of or active autoimmune disease. Persons with vitiligo or thyroid disease taking thyroid replacement are not excluded. Persons with rheumatoid arthritis not requiring immunomodulatory and/or immunosuppressant treatment are not excluded.
5. Known or suspected impairment of immunologic functions including, but not limited to chronic inflammatory bowel disorders, diabetes mellitus type I.
6. History of malignancy other than squamous cell or basal cell skin cancer, unless there has been surgical excision at least 6 months ago that is considered to have achieved cure. Subjects

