**Figure 3**      **Algorithm for Cardiac Follow-up**

## 8.2.10 Safety Laboratory Measurements

The intensity of laboratory / systemic toxicities measured quantitatively will be graded according to the toxicity scale in [Appendix 1: Toxicity Scale for Laboratory Values](#). These grading scales include the laboratory values determined with the routine safety parameters. In case of other laboratory values not included in the routine safety laboratory and not listed in [Appendix 1: Toxicity Scale for Laboratory Values](#), the Toxicity Grading Scale for Healthy Adult and Adolescent Volunteers Enrolled in Preventive Vaccine Clinical Trials (Guidance for Industry, U.S. Department of Health and Human Services, Food and Drug Administration (FDA), Center for Biologics Evaluation and Research, September 2007) will be used for grading of laboratory toxicities.

Safety laboratory is determined at screening, Visit 2 and Visit 4 in the main trial and at BV0 and BV2 during the booster substudy and at any other visit(s) if clinically indicated. The safety laboratory measurements are performed at a central laboratory. Laboratory normal ranges are provided by the central laboratory and filed in the Investigator File. Safety laboratory parameters to be evaluated are:

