## Appendix 1: Toxicity Scale for Laboratory Values

Grade 1 or Grade 2 toxicity is only graded according to [Table 15](#), [Table 16](#) and [Table 17](#) if the value is outside of the institutional normal range applicable for this trial. Any laboratory value that is between either the Lower Limit of Normal (LLN) or Upper Limit of Normal (ULN) and Grade 1 should not be graded. The values provided in [Table 15](#), [Table 16](#) and [Table 17](#) are based on the Toxicity Grading Scale for Healthy Adult and Adolescent Volunteers Enrolled in Preventive Vaccine Clinical Trials, (Guidance for Industry, U.S. Department of Health and Human Services, Food and Drug Administration, Center for Biologics Evaluation and Research, September 2007).

For abnormalities NOT found elsewhere in the Toxicity Tables, use the scale below to estimate grade of severity:

- Grade 1** An AE which is easily tolerated by the subject, causing minimal discomfort and not interfering with daily activities.
- Grade 2** An AE which is sufficiently discomforting to interfere with daily activities.
- Grade 3** An AE which prevents daily activities. Such an AE would, for example, prevent attendance at work and would necessitate the administration of corrective therapy.
- Grade 4** Life-threatening, hospitalization or disabling.

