**Table 17    Grading for Troponin I**

Lab Value	Mild (Grade 1)	Moderate (Grade 2)	Severe (Grade 3)	Potentially Life Threatening (Grade 4)
Cardiac troponin I	> ULN-< 2 x ULN	≥ 2-< 5 x ULN	≥ 5 x ULN	N/A

“ULN” is the upper limit of the normal range.

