### **3.5.9 Clinical Laboratory Exams (Hematology, Chemistry)**

All measured hematology and chemistry values (and changes from baseline for continuous parameters) will be listed and summarized at each sampling visit using descriptive statistics (mean, SD, median, Min and Max).

Summary tables will be produced for the number of high and low laboratory values at Screening Visit, Visit 2 and Visit 4 by hematology and chemistry parameter. Note that Hepatitis B and C testing, HIV testing, and Troponin I testing are only summarized at the Screening Visit.

Study specific version: 1.0  
Study specific version Date: 31-May-17

In addition, all clinical laboratory values outside the normal range will be listed by subject, gender, age and flagging of abnormal values (LN=Below normal range, HN=Above normal range) with their clinical significance.

Shift tables will be used to evaluate categorical changes from Screening Visit to Visit 2 and Screening Visit to Visit 4 with respect to normal ranges (below LLN, Normal, above ULN) in hematology and biochemistry parameters.

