### 4.5.9 Clinical Laboratory Exams (Hematology, Chemistry)

All measured hematology and chemistry values (and changes from booster baseline for continuous parameters) will be listed and summarized at each sampling visit using descriptive statistics (mean, SD, median, Min and Max).

Summary tables will be produced for the number of high and low laboratory values at BV0, booster baseline, BV2 and BEAP by hematology and chemistry parameter.

In addition, all clinical laboratory values outside the normal range will be listed by subject, gender, age and flagging of abnormal values (LN=Below normal range, HN=Above normal range) with their clinical significance.

Shift tables will be used to evaluate categorical changes from booster baseline to BV2 with respect to normal ranges (LN, Normal, HN) in hematology and biochemistry parameters.

Booster baseline is defined as last available measurements prior to the booster vaccination. This will be different from the booster screening measurement when the subject has missing screening value or has multiple screening values.

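### Laboratory toxicities are graded, but the SAPs provided plan no summary or shift table by grade, so Grade 1-to-2 worsening shows as no change in the shift tables

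*Protocol*

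**What the plan says.** Protocol 8.2.10 sets the grading rule: "The intensity of laboratory / systemic toxicities measured quantitatively will be graded according to the toxicity scale in" Appendix 1. The appendix limits it in two ways. Grades 1 and 2 apply only "if the value is outside of the institutional normal range applicable for this trial", and a value lying "between either the Lower Limit of Normal (LLN) or Upper Limit of Normal (ULN) and Grade 1 should not be graded".

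The protocol uses the grade in several places:
- **Entry.** Main-trial inclusion criterion 7 reads "Not clinically significant laboratory values as defined in the protocol, excluding any Grade" 3 or higher.
- **AE recording.** Under 8.1.2.1, Grade 3 and 4 values after the first vaccination are recorded as AEs whether or not they are thought relevant. Lower-grade abnormal values become AEs only if the investigator finds them clinically significant.
- **Halting.** Section 4.5 refers to Grade 3 or higher laboratory toxicity.

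The analysis text does not use it for laboratory tables. Protocol 9.3.2 marks each result as below, within or above range and adds: "The number of values outside of the corresponding reference range will be counted". Main SAP 3.5.9 takes its shift categories from the reference range: "Shift tables will be used to evaluate categorical changes from Screening Visit to Visit 2 and Screening Visit to Visit 4 with respect to normal". Booster SAP 4.5.9 states: "Shift tables will be used to evaluate categorical changes from booster baseline to BV2 with respect to normal ranges (LN, Normal, HN"). Both SAPs also summarise values and changes from baseline (mean, SD, median, Min, Max), count high and low results, and list out-of-range values with clinical significance. The planned laboratory tables (14.3.3.1 to 14.3.3.6 and 15.3.3.1 to 15.3.3.6) cover means, abnormalities and shifts; no title mentions grade.

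**The concern.** A shift table is meant to show, by group, how many subjects changed for the worse. With three categories it shows only movement into or out of the normal range. Anyone already out of range at screening or booster baseline can worsen on that side without leaving the cell.

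Such subjects can be enrolled. Participants are 55 or older, and a Grade 1 or 2 value that is not clinically significant does not bar main-trial entry. The booster criteria set no numerical laboratory limit and rely on investigator judgement.

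Increased potassium was the second most frequently reported unsolicited event in the Phase I trial (Protocol 2.6). The higher dose here, 5 x 10^8, is five times the top Phase I dose of 1 x 10^8. A between-group difference in mild-to-moderate laboratory worsening is the kind of signal a grade table would display and these shift tables would not.

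**Working it through.** The plan states no figure to reproduce here. The check maps grades onto the shift-table categories.

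**Step 1: which category a grade falls in.** By Appendix 1, Grades 1 and 2 exist only outside the normal range. A graded 1-then-2 result on the high side is therefore above range both times, and on the low side below range both times.

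**Step 2: count the worsening steps on one side.** Let 0 be normal and 1 to 4 the grades.
- All worsening steps: 4 + 3 + 2 + 1 = 10.
- Visible in a normal/high table: 0 to 1, 2, 3 or 4 = 4 steps.
- Hidden: 10 - 4 = 6 (1-2, 1-3, 1-4, 2-3, 2-4, 3-4).
- With entry at Grade 2 or below, 3-4 cannot occur from baseline: 9 steps, 5 hidden.
- Of those 5, the steps ending in Grade 3 or 4 are 1-3, 1-4, 2-3 and 2-4 = 4. All are automatic AEs.
- Remaining without an automatic record: 5 - 4 = 1, the step from Grade 1 to Grade 2.

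In the booster substudy, which has no numerical laboratory limit, the sixth hidden step (3-4) is also possible. It ends in Grade 4 and so is also an AE. The count leaves out values that are out of range but ungraded. Moves from there to Grade 1 or 2 also stay in the same cell.

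**Step 3: an example from Table 15.** High potassium is Grade 1 at 5.1-5.2, Grade 2 at 5.3-5.4, Grade 3 at 5.5-5.6 and Grade 4 above 5.6 mmol/L. Take 5.1 at screening and 5.4 at Visit 2. The central laboratory's upper limit is not given, so it is assumed:

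| Assumed ULN | 5.1 | 5.4 | Shift shown |
|---|---|---|---|
| 4.9, 5.0 or 5.05 | above range, Grade 1 | above range, Grade 2 | High to High |
| 5.3 | in range, not graded | above range, Grade 2 | Normal to High |

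Wherever the first value truly carries Grade 1, the shift is hidden.

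**Step 4: where else the step could appear.**
- *AE tables:* only if judged clinically significant.
- *Listings:* yes, but without a comparison between groups.
- *Min and Max:* one extreme value per group and visit, with no count of subjects and no starting grade.
- *Means:* diluted. As an assumption only, suppose 5% to 15% of 80 subjects are out of range at entry: 0.05 x 80 = 4 to 0.15 x 80 = 12. Suppose half of these go from Grade 1 to Grade 2: 2 to 6. If each rises by 0.3 mmol/L, the group mean moves by 2 x 0.3 / 80 = 0.0075 to 6 x 0.3 / 80 = 0.0225 mmol/L, while the shift table records no shift for these subjects. The 4 to 12 is a ceiling on Grade 1 entrants, because some out-of-range values are ungraded or already Grade 2.

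**The case against.** The best case against is that little is lost. Both SAPs summarise values and changes from baseline by group with Min and Max, and list out-of-range values. Severe worsening is caught: Grade 3 and 4 values are AEs and enter the Grade 3-or-higher tables, and the AE overview has a row for Grade 2 or higher, so a clinically significant Grade 2 value is counted there. A step from Grade 1 to Grade 2 can be one unit, as with sodium 146 to 147 mmol/L. No listed safety endpoint is a laboratory grade or shift. All of this stands, and it makes the point an improvement in reporting rather than a failure of safety monitoring.

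It also rules out several stronger readings that a reader might infer:
- *Every laboratory value has a four-grade scale.* Out-of-range values short of Grade 1 are ungraded, troponin I has no Grade 4, and red cell count, hematocrit, MCV, MCH, MCHC and RDW have no row in Tables 15 to 17.
- *Only low/normal/high is analysed, so an effect below Grade 3 cannot be seen.* The continuous summaries contradict this.
- *Large elevations vanish into the High cell.* ALT at 8 x ULN lies in Grade 3 (5.1-10.0 x ULN) and is an automatic AE after the first vaccination.
- *Main-trial entry is limited only by Grade 3.* Criterion 7 also requires values that are not clinically significant.
- *Repeat and unscheduled results go to listings only.* Main SAP 3.5.1 and booster SAP 4.5.1 say they are listed; neither says they are kept out of tables. The shift tables are, however, defined at fixed visits.
- *Sections 8.2.10 and 9.3.2 contradict each other.* They do not; the grade is used for entry, AE recording and halting.

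What the objection does not supply is any planned table that counts, by group, subjects who worsened in grade.

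**Conclusion.** The point holds in limited form. In Protocol 9.3.2 and the two SAPs provided, no laboratory summary or shift table is by toxicity grade. Among graded worsening steps, Grade 1 to Grade 2 is the one that the shift tables show as unchanged and that has no automatic AE record.

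The structural result needs no assumed rate. How many subjects it affects is unknown: the documents give neither the frequency of out-of-range values at entry nor the central laboratory's ranges, and the 5% to 15% used above is only illustrative.

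One condition applies. Booster SAP section 1 refers to a main-study SAP Addendum of 11 October 2017 and to table shells in a separate document. Neither was available, and a grade table there would settle the matter for the study it covers.

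**What to change.** In main SAP 3.5.9 and booster SAP 4.5.9, keep the low/normal/high shift tables and add, for each parameter with an Appendix 1 grade, a table by treatment group that shifts from baseline grade (screening, or booster baseline) to worst post-vaccination grade. Specify that:
- out of range but ungraded is its own category;
- direction is shown where both low and high values are graded, as for sodium, potassium and calcium;
- repeat and unscheduled samples count toward the worst grade.

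The grade table should not replace the existing ones. Without them, and without the ungraded category, moves from normal to out of range but ungraded would disappear, and parameters with no grade would have no shift table.

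The cost is SAP wording and programming of a few more tables; the values, ranges and scale already exist. Some cells will be sparse. With one mandatory safety sample after each vaccination (Visits 2 and 4; BV2 for the booster), the worst grade will often simply be the scheduled one.

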## 10 Ethical Aspects

### 10.1 Ethical and Legal Regulations

The PI is to ensure that this clinical trial is conducted in complete accordance with the provisions of the 2013 version of the Declaration of Helsinki, the national laws and other guidelines for the conduct of clinical trials like the ICH GCP to guarantee the greatest possible subject protection.

### 10.2 Approval by an IEC/IRB and IBC

The clinical trial protocol must be reviewed by the competent IEC/IRB according to the national laws of the respective CTS before the first subject is included in this trial.

If one of the investigators is a member of one of these committees, he/she may not vote on any aspect of the review of this protocol.

The Sponsor will assure that the IEC/IRB is informed of any amendment to the protocol and any unanticipated problems involving risks to human subjects included in the trial. Such information will be provided to the IEC/IRB at intervals appropriate to the degree of subject risk involved, but not less than once a year. Copies of all correspondence between the investigator and the IEC/IRB must be forwarded immediately to the Sponsor. In case of withdrawal of IEC/IRB approval of the trial, the Sponsor has to be contacted immediately by facsimile, e-mail or telephone.

The MVA-BN-RSV vaccine meets the exemption criteria set forth in Appendix M-VI-A of the NIH Guidelines for Research Involving Recombinant or Synthetic Nucleic Acid Molecules and is therefore exempt from the requirements of submission of the protocol to NIH OBA (Office of Biotechnology Activities), RAC (Recombinant DNA Advisory Committee) review and subsequent reporting but is expected to follow all other requirements of the NIH Guidelines. This includes having the protocol reviewed and approved by the responsible Institutional Biosafety Committee (IBC) for each site before research participants are recruited.

### 10.3 Confidentiality and Data Protection

The PI of the respective CTS is obliged to ensure anonymity of the subject. He/she has to make sure that all documents including eCRFs provided (e.g. in the course of a marketing authorization procedure) to third parties (in this case: to the manufacturer of MVA-BN-RSV vaccine or to an authority) contain no subject names.

Only a subject and site number may identify subjects. Their name or clinic and subject's medical record number may not be used. The PI keeps separate confidential subject logs for trial recruitment which allows subject numbers to be matched with names and addresses of subjects at any time. Documents not meant to be passed on to third parties have to be stored securely by the PI.

Any information collected in the course of the trial may be made available only to persons directly involved in this trial (PI and his staff members, monitors, statisticians) or to persons authorized by the Sponsor or the PI or to authorities. The Sponsor of the trial will only receive pseudonymized data for analysis.

## 11 Informed Consent

No subject can participate in this trial without having given informed consent in writing after the investigator or his delegate has informed the subject clearly and completely, verbally and in writing, over the purpose, procedures, the potential future use of blood samples (see [Section 7.4](#)) and potential benefits and risks of the trial prior to any trial specific procedure.

One signed copy of the Informed Consent including HIPAA must be given to each subject and one signed copy must remain in the Investigator Site File and be available for verification by the monitor, Sponsor/CRO auditor or competent regulatory authorities at any time.

Subjects must be informed unequivocally that they may refuse participation in the trial and that they may withdraw from the trial at any time and for whatever reason and that withdrawal of consent will not affect their subsequent medical treatment or relationship with the treating physician.

Subjects also consent to authorize the monitor, quality assurance personnel and regulatory authorities to inspect source documents for data verification and quality assurance purposes. Such verifications will always be conducted at the CTS and under the ethical supervision of the investigator. All aspects of the confidentiality of the subject's data will be guaranteed.

Subjects eligible for the booster substudy have to sign a new ICF at BV0.

The Informed Consent will be prepared in accordance with ICH GCP guidelines and must be approved by the appropriate IEC/IRB.

## 12 eCRF, Retention of Records and Monitoring

### 12.1 eCRF

In this trial, the use of an eCRF is planned.

All eCRFs are to be filled out completely by the trial personnel, then reviewed and signed electronically by the PI to confirm their correctness in a timely manner. It is the PI's responsibility to ensure that all subject data entered in the eCRF (including discontinuations or changes in trial vaccine or other medications) are accurate and supported by the subject's medical records unless the eCRF has been declared as source documentation by BN. The eCRFs for any subject leaving the trial should be completed at the time of the final visit or shortly thereafter.

For subjects not fulfilling the eligibility criteria the minimum information documented in the eCRF is the ICF information, demographics and reason for screen failure.

